7.10. Safety Evaluation

To monitor safety, subjects will be asked at each visit and during telephone contacts about changes in their medical conditions. Adverse events should be assessed in terms of their seriousness, duration, intensity, and relationship to the study device. All anticipated and unanticipated adverse events will be collected. Subjects will be able to contact the investigator at any time during the study if they note any change in their medical condition. The outcome of each adverse event will be observed and documented.

Safety analysis, including adverse events and device deficiencies incidence and description will be run on FAS only.

a. Adverse Events Definitions and Reporting Requirements

An adverse event (AE) is any complaint or untoward medical occurrence that is an unintended disease or injury or untoward clinical sign (including abnormal laboratory findings) in a subject, users or other persons, whether or not related to the investigational medical device. AEs are non device related, non serious medical occurrences.

A Serious adverse event (SAE) is an untoward medical occurrence in a subject that is not related to the investigational device, comparator, or trial procedures, but that meet the criteria of "serious". A Serious Adverse event is one that:

- Led to a death
- Led to a serious deterioration in the health of the subject that:
 - resulted a life-threatening illness or injury;

- resulted in permanent impairment of a body structure or body function and required inpatient hospitalization or prolongation of existing hospitalization;
- resulted in medical or surgical intervention to prevent life threatening illness or permanent impairment to body structure or body function.
 - Led to fetal distress, fetal death, congenital abnormality or birth defect.

An Adverse Device Effect (ADE) is an occurrence related to or caused by the investigational device, procedure or comparator that is not serious.

A Serious Adverse Device Effect (SADE) is an adverse device effect, comparator, or procedure that has resulted in any of the consequences characteristic of a serious adverse event and is serious, but is not unanticipated.

An Unanticipated Serious Adverse Device Effect (USADE) (also called an unanticipated device effect in per 21 CFR Part 812) is any medical occurrence or unintended disease or injury or serious adverse effect (including abnormal laboratory findings) on health or safety or any life-threatening problem or death caused by, or associated with, a device, if that effect, problem, or death was not previously identified in nature, severity, or degree of incidence in the investigational plan or application, or any other unanticipated serious problem associated with a device that relates to the rights, safety, or welfare of subject.

Adverse events will be collected and documented until the end of the study.

All adverse events will be graded as follows:

- Mild: Sign or symptom, usually transient, requiring no special treatment and generally not interfering with usual activities.
- Moderate: Sign or symptom, which may be ameliorated by simple therapeutic measures, may interfere with usual activity.
- Severe: Sign or symptom that are intense or debilitating and that interfere with usual activities. Recovery is usually aided by therapeutic measures and the discontinuation of the study device

may be required.

The relationship of the adverse event to the study is defined as follows:

- Definitely: an adverse event was shown to be related to the study device
- Probable: an adverse event has a strong temporal relationship to study device, and another etiology is unlikely or significantly less likely.
- Possible: an adverse event has a strong temporal relationship to the study device, and an alternative etiology is equally or less likely compared to the potential relationship to study device.
- Unlikely: an adverse event has little or no temporal relationship to the study device and/or a more likely alternative etiology exists.
- Not assessable: Given the information available, sequence and timing of events, it is unknown or impossible to determine the relationship of the adverse event with the study device.
- None: an adverse event has no temporal relationship to study device or has a much more likely alternative etiology.

b. Device Deficiency

Since device deficiencies are not captured on study eCRF they will not be included in this analysis

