- Between 5-28 days (visit 4) after SPM and gastric scintigraphy test day- 3 management plans based first on one motility test blinded to the second test and then independently based on second test but not blinded to the first test result. The PI will then develop a third patient management plan based on both test results. This plan will be presented to the patient at the follow-up visit (visit 4)

Subjects will be contacted at 3 and 6 months post SPM procedure for follow-up assessment of symptoms.

Subjects will be compensated for completing the study.

All observations/ assessments to be conducted are displayed in the Trial Flow Chart (Appendix- A of Protocol) and detailed in the sections below

Study Duration: each subject is expected to participate in the study for two to five weeks (including medication wash) and up to 6 months follow up. Each subject will report to the study site for at least 4 visits and up to 6 visits.

Up to 16 months will be required to enroll 275 patients following IRB approval of the study. The completion of the study will require 20 months due to data collection and validation, data analysis, and the final clinical report.

Inclusion criteria

- Males and females between ages of 18-80 years of age with symptoms of gastroparesis for at least 12 weeks.
- Presenting with 2 or more of the following symptoms or signs which, in the opinion of the site investigator, are suggestive of a diagnosis of gastroparesis:
 - .1 Nausea, vomiting, or retching (dry heaves)
 - .2 Postprandial fullness or early satiety
 - .3 Bloating or visible abdominal distention
 - .4 Postprandial discomfort or pain
- Ability to stop proton pump inhibitors for 7 days and histamine₂ receptor antagonists, prokinetic agents, narcotic agents, anticholinergic drugs, and cannabinoids 3 days prior to SPM and gastric scintigraphy testing.
- No evidence of metabolic disease (hypothyroidism, uncontrolled diabetes [hemoglobin A1c >10% within the past 6 months], electrolyte imbalance).
- An upper endoscopy or upper gastrointestinal barium series within the past 2 years showing no organic disease that is potentially causative of symptoms.
- High probability of compliance and completion of study.

Exclusion criteria

- Participation in previous SmartPill clinical trials.
- Previous history of bezoars (the presence of retained liquid, bile, or small amounts of poorly organized food residue is permitted).
- Dysphagia to solid food or pills.

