- Prior surgery involving the luminal gastrointestinal tract (cholecystectomy, appendectomy, and hysterectomy are permitted if performed > 3 months prior to SPM test).
- Any abdominal or pelvic surgery within the past 3 months
- Known or history of inflammatory bowel disease.
- History of diverticulitis, diverticular stricture, and other intestinal strictures.
- Chronic daily use of nonsteroidal anti-inflammatory drugs (ibuprofen, naproxen, etc.)
- Tobacco or alcohol use within eight hours prior to capsule ingestion.
- BMI > 40 kg/m².
- Allergies to eggs, bread, or jam.
- Females of childbearing age who are not practicing birth control and/or are pregnant or lactating. (Urine pregnancy testing will be performed on female subjects of child-bearing potential prior to capsule ingestion and gastric scintigraphy).
- Use of cardiac medical devices such as pacemakers and defibrillators (gastric stimulators, bladder stimulators, spinal stimulators, medication infusion devices, insulin pumps, continuous glucose monitors are permitted).
- Uncontrolled diabetes with a hemoglobin A1c >10%.
- Patient is expected to undergo MRI examination within 7 days after ingestion of the capsule

Prohibited Medications

Medications Which May Alter Gastric pH:

- (i) Proton pump inhibitors (omeprazole, lansoprazole, esomeprazole, dexlansoprazole, pantoprazole, rabeprazole) for 7 days prior to study including the day of SPM ingestion.

- (ii) Histamine₂ receptor antagonists (cimetidine, ranitidine, famotidine, nizatidine) for 3 days prior to study including the day of SPM ingestion.
- (iii) Antacids (containing magnesium, aluminium, or calcium carbonate) for 1 day prior to study including the day of SPM ingestion.

Medications That May Affect Gastrointestinal Motility: The following medications must be discontinued for 3 days prior to study including the day of SPM ingestion (if subject develops nausea to the degree that study discontinuation is contemplated, he or she may take promethazine, prochlorperazine, or ondansetron as rescue antiemetics in doses recommended by the site investigator):

- (i) Prokinetic agents (metoclopramide, domperidone, erythromycin, azithromycin, bethanechol, pyridostigmine)
- (ii) Narcotic analgesics (codeine, hydrocodone, oxycodone, methadone, fentanyl, etc.)
- (iii) Anticholinergic agents (dicyclomine, hyoscyamine, scopolamine)
- (iv) Cannabinoids (dronabinol, marijuana)

Permitted Medications

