7.1. Study Subjects

7.1.1. Disposition of Subjects

Enrolled patients (Full Analysis Set) will be summarized using frequencies and percentages from the screened population.

Protocol deviations will be summarized and listed, and per-protocol patients will be summarized (frequency and percentage from Full Analysis Set population).

Frequency and percentage of FAS patients with full follow-up will be reported, as well as patients with early withdrawal from the study, and the related reasons. Please refer to section 7.1.3

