7.1.3. Analysis Sets

Two analysis sets will be created for study purpose:

1. Full Analysis Set (FAS). FAS includes all enrolled subjects:

- who signed the informed consent and
- who satisfied to the eligibility criteria

FAS will be used for subjects disposition, population description, and for Safety analysis.

2. Per Protocol Analysis set (PPAS): PPAS is a subset of the FAS, restricted to subjects who adhere to the protocol, in terms of SPM and Scintigraphy procedures, and minimal follow-up.

Two subsets of the PPAS - according to follow-up- will be created and used for Performance analysis purpose:

- PPAS1: Subjects who completed the full study follow up to 6 months FU
- PPAS2: Subjects who completed visit 4 with 3 patient management plans- this group will be larger than the above and will have all data for study end points, even though not completed full study flow.

Listing of major protocol deviations to be excluded from the PPAS1 and 2 will be provided by the study team prior to run statistical analysis.

Per protocol Analysis Sets (PPAS1 and PPAS2) will be used for Performance analyses.

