7.2. General Methodology

Continuous variables will be summarized using tables of descriptive statistics: number of patients with recorded observations, mean, standard deviation, median, minimum and maximum. Categorical variables will be summarized using counts and percentages. Descriptive statistics will be presented by diagnosis and clinical center. Diagnostic outcome will be tabulated and compared for SPM and conventional test and percentage gain determined. Frequency of patient management change resulting from SPM test relative to conventional test will be recorded for categories of: therapy, elimination of diagnostic testing, diet and surgery.

Statistical analysis will consist in:

- Descriptive analysis of patients characteristics and assessments before and after study procedures.
- Agreement analyses between SmartPill Motility Monitoring System and Gastric Scintigraphy (GS)
- Correlation analysis between PAGI-SYM, PAGI-QOL and SPM and GES.
- Descriptive and Comparative analysis of safety parameters related to procedures, between SPM and GES.

Parameters ascribed to the safety of patients will be summarized by diagnosis and clinical center.

All available data from patients who fail to complete this study will be included in all safety summaries.

Agreement analysis (primary and secondary endpoints) will be run to provide % of agreement (overall, positive and negative agreement) between both procedures, as well as Kappa coefficient, p-value and 95% confidence interval.

Correlation analysis (between two quantitative parameters) will be run: Pearson coefficient, p-value and 95% confidence interval will be calculated.

For other analyses:

- Continuous variables will be summarized using descriptive statistics, specifically the mean, standard deviation, median, minimum and maximum. Comparison of continuous parameters between two groups will be performed using T-test or Wilcoxon Man-Whitney U test, or Wilcoxon signed rank test (non-parametric) for paired data, as appropriate.
- Categorical variables will be summarized using frequencies and percentages, and compared between two groups using Chi-Square or Fisher exact test, or Mac Nemar Chi-square test for paired data, as appropriate.

Subject disposition and follow-up, as well as demographic and baseline characteristics of patients, results related to SPM and GES , or to any questionnaire will be described for each clinical center.

Reporting outputs

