7.12. Changes to Planned Analysis

Per protocol, final statistical analysis was scheduled once N=275 patients were enrolled and completed the study ; due to sponsor decision upon interim analysis primary endpoint results, decision have been taken to early stop the enrollment at N=167 subjects. So, final statistical analysis will be run on N=167 enrolled subjects.

8. Validation Requirements

Original Statistical Programmer performs a visual inspection of the code and output to confirm functionality (Level III as per 056-Wi 181).

9. References

2. De La Loge C, Trudeau E, Marquis P et al. Responsiveness and interpretation of a quality of life questionnaire specific to upper gastrointestinal disorders. Clin Gastroenterol Hepatol. 2004 Sep;2(9):778-86.

10. Statistical Appendices

N/A

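### The serious-event list lacks stand-alone criteria for hospitalisation and for permanent impairment, and the SAP's sections disagree on whether safety covers subjects found ineligible

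*SAP*

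**What the plan says.** **Seriousness.** SAP section 7.10(a) lists the outcomes that make an event serious: death; a serious deterioration in health of one of three kinds; or a fetal or congenital outcome. The three kinds of deterioration are (a) life-threatening illness or injury, (b) permanent impairment *and* inpatient hospitalisation or its prolongation, and (c) an intervention made to prevent life-threatening illness or permanent impairment. A serious adverse device effect (SADE) is defined by the same consequences. The unanticipated category (USADE) has its own, broader wording. The section describes AEs as non-serious and adverse device effects (ADEs) as not serious.

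**Population.** Section 7.1.3 admits to the FAS enrolled subjects who consented and "who satisfied to the eligibility criteria", and adds: "FAS will be used for subjects disposition, population description, and for Safety analysis". Section 7.10 repeats the restriction: "Safety analysis, including adverse events and device deficiencies incidence and description will be run on FAS only". Section 7.1.1 uses the same label without an eligibility condition: "Enrolled patients (Full Analysis Set) will be summarized using frequencies and percentages from the screened population". Section 7.2 adds: "All available data from patients who fail to complete this study will be included in all safety summaries". No other safety set is defined.

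**Device deficiencies.** The section 7.10 sentence includes their incidence. Subsection 7.10(b) says they are left out because the case report form does not collect them.

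**The concern.** The seriousness list decides which events appear in the SAE and SADE tables. If hospitalisation counts only together with permanent impairment, an admission from which the subject recovers is reported as non-serious unless another criterion catches it. The same holds for a lasting impairment managed without admission. The Introduction (section 3) says this disease leads to heavy use of inpatient care, so admission without lasting impairment is a foreseeable event here.

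The population rule decides whose events are counted at all. An eligibility condition on a safety set can remove a subject who swallowed the capsule or the radiolabelled meal, together with any event that followed. The main risk is the lost event. The change in denominator is small.

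The device-deficiency sentence commits the report to an incidence that the next subsection says will not be produced.

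**Working it through.** The plan states no figure on this point, so there is none to reproduce. The check is one of definitions, followed by an illustration on assumed counts.

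**Step 1: the joined bullet.** The and/or can be grouped in two ways.

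| Outcome on its own | Impairment AND (hospitalisation OR prolongation) | (Impairment AND hospitalisation) OR prolongation |
|---|---|---|
| New hospitalisation | not serious | not serious |
| Permanent impairment | not serious | not serious |
| Prolonged hospitalisation | not serious | serious |

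The grouping matters only for prolongation. A new hospitalisation alone and permanent impairment alone fail under both.

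**Step 2: do the other criteria fill the gap?** Death, life threat and fetal outcomes catch only events of those kinds. The intervention criterion needs an intervention meant to *prevent* life-threatening illness or impairment. It therefore catches some admissions, but not those without such an intervention, and not impairment that has already occurred.

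**Step 3: where the event goes.** It is not lost from the data. It moves from SAE to AE, or from SADE to ADE. Each such event lowers the serious count by one. The number is not given and may be zero.

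**Step 4: who is in safety, section by section.**

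| Enrolled, consented subject | 7.1.3 with 7.10 | 7.1.1 label | 7.2 |
|---|---|---|---|
| Eligible, tested, completes | in | in | not addressed |
| Tested, later found ineligible, completes | out | in | not addressed |
| Tested, later found ineligible, does not complete | out | in | non-completers in; silent on eligibility |
| Eligible, withdraws before testing | in | in | in |

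The second row is the clear conflict.

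**Step 5: illustration.** Section 7.12 gives the enrolled number: "final statistical analysis will be run on N=167 enrolled subjects". The rest is assumed, because the SAP gives neither the number ineligible nor the number tested, and the 167 are taken to include any subject later found ineligible.

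- Tested but ineligible completers at 0%, 2% or 5%: 167 × 0.02 = 3.3, taken as 3; 167 × 0.05 = 8.4, taken as 8. The FAS is then 167, 164 or 159.
- Never tested at 0%, 5% or 10%: 167 × 0.05 = 8.4, taken as 8; 167 × 0.10 = 16.7, taken as 17. The tested number is then 167, 159 or 150.
- Rate = k/n, with Clopper-Pearson 95% limits. For k = 0 the upper limit is 1 − 0.025^(1/n).

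| Case | Set | Result (95% CI) |
|---|---|---|
| One event, in a tested but ineligible completer | all enrolled | 1/167 = 0.60% (0.02 to 3.29) |
| | tested, n = 159 | 1/159 = 0.63% (0.02 to 3.45) |
| | tested, n = 150 | 1/150 = 0.67% (0.02 to 3.66) |
| | FAS, 3 removed | 0/164 = 0% (0 to 2.22) |
| | FAS, 8 removed | 0/159 = 0% (0 to 2.29) |
| Three events, none lost | all enrolled | 3/167 = 1.80% (0.37 to 5.16) |
| | FAS, 3 removed | 3/164 = 1.83% (0.38 to 5.25) |
| | FAS, 8 removed | 3/159 = 1.89% (0.39 to 5.41) |
| | tested, n = 150 | 3/150 = 2.00% (0.41 to 5.73) |

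When no event is lost, the rates stay between 1.80% and 2.00%. With nobody ineligible and nobody untested, there is no difference at all.

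**The case against.** **On seriousness.** The SAP was written after the June 2015 interim analysis and after the decision to stop enrolment (sections 7.8 and 7.12). Many events had presumably been assessed by then, and the definition that governed them is normally in the protocol, which is not shown. This stands: a reader might infer that serious events were undercounted, but the SAP shows only a faulty definition. The USADE wording does not use the joined list and can take in an unanticipated device-related hospitalisation. That also stands, and narrows the device-related gap to anticipated effects. The intervention criterion catches some admissions too. None of this gives hospitalisation or permanent impairment a criterion of its own in the SAE and SADE definitions.

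**On the population.** Sections 7.1.1 and 7.1.3 can be read together naturally: eligibility is the gate to enrolment, so enrolled and FAS are the same 167. On that reading nobody is dropped. Exclusion needs the literal reading, but the eligibility condition is written as a condition on top of enrolment, so the text should settle the matter.

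Three stronger readings are tempting and not supported.

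- *That subjects are bound to be found ineligible after testing.* Section 5 says "each subject is expected to participate in the study for two to five weeks (including medication wash", and one exclusion is "Tobacco or alcohol use within eight hours prior to capsule ingestion", so eligibility can fail after participation begins. But the criterion concerns the time before ingestion, and the same list places pregnancy testing before ingestion. That a failure would surface only after the test is conjecture, and the SAP describes no such subject.
- *That section 7.2 expressly keeps ineligible non-completers.* It does not mention eligibility.
- *That safety should be confined to subjects who ingested something.* That would drop events in subjects who withdrew during the medication wash, which section 5 counts as participation. Keeping untested enrolled subjects in overall safety is defensible.

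**On device deficiencies.** The specific subsection explains the omission, so the conflict is editorial.

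**Conclusion.** The point holds in three parts of unequal weight.

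1. The serious-event list is wrong as written. Under either grouping, a new hospitalisation alone or permanent impairment alone is not serious unless another criterion applies, and SADE inherits this. Whether any count is too low depends on whether events were classified under this wording, which the SAP does not say.
2. The safety population is inconsistently defined. Read literally, sections 7.1.3 and 7.10 leave out a tested, ineligible completer whom section 7.1.1 would include. The consequence is a possible lost event; the denominator effect is small even on the assumed counts. The number of such subjects is not given and may be zero.
3. The device-deficiency conflict needs only an edit.

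The first part rests on the text alone. For the second, the numbers rest on assumed counts and show only what kind of effect is possible.

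**What to change.** - **Section 7.10(a):** list permanent impairment, and inpatient or prolonged hospitalisation, as two separate criteria. Reconcile the list with the protocol definition under which events were classified. If the joined wording was used, re-check the seriousness of recorded events.
- **Sections 7.1.1, 7.1.3, 7.2 and 7.10:** run overall safety on all enrolled, consented subjects regardless of eligibility, so that events during the medication wash and in non-completers stay in. Report device- and procedure-related event rates on the subset who ingested the capsule or the radiolabelled meal, also regardless of eligibility. Use the same terms in all four sections.
- **Section 7.10, opening sentence and subsection (b):** remove device deficiencies from the sentence, or name the source from which they will be reported.

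The cost is SAP wording, one added subset for the related-event tables and, only if the joined wording was applied, a re-check of recorded events. Serious counts may rise as a result.

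### SAP section 7.10 defines adverse events in two incompatible ways and restricts SAEs to unrelated events, so the content of the AE incidence is undetermined and an SAE count is not a count of all serious events

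*SAP*

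**What the plan says.** All the definitions stand in SAP section 7.10, subsection a.

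- **AE, first sentence:** any untoward occurrence, "whether or not related to the investigational medical device".
- **AE, next sentence:** "AEs are non device related, non serious medical occurrences".
- **SAE:** a serious event that "is not related to the investigational device, comparator, or trial procedures".
- **ADE:** "An Adverse Device Effect (ADE) is an occurrence related to or caused by the investigational device, procedure or comparator that is not serious".
- **SADE:** worded as a kind of adverse device effect, but one whose consequences are "characteristic of a serious adverse event and is serious, but is not unanticipated".
- **USADE:** an unanticipated serious effect caused by or associated with a device. It extends to other unanticipated serious problems that bear on subjects' rights, safety or welfare.

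The opening of section 7.10 also asks that adverse events be assessed for seriousness and for relationship to the study device. Subsection a grades that relationship on six levels, from Definitely to None, with a separate Not assessable level.

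The analysis itself is stated in one sentence: "Safety analysis, including adverse events and device deficiencies incidence and description will be run on FAS only". Section 7.2 adds a descriptive and comparative analysis of procedure-related safety parameters between SPM and scintigraphy.

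**The concern.** An SAP that restates the event classes has to restate them so that a programmer can assign each event and total it in one way only. Here two consecutive sentences give different contents to the same term, and the one sentence that describes the safety analysis uses that term without saying which sense it means. It also does not say whether ADE, SADE and USADE are counted in the same total or tabulated separately.

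In a device study, the events related to the device or to the procedures are the ones a reader of the safety section looks for first, and the comparison of SPM with scintigraphy in section 7.2 depends on them. Two programmers could follow section 7.10 and produce different AE totals. A reader who sees an SAE count would take it for the number of serious events, which by this definition it is not.

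**Working it through.** The plan gives no figure on this point, so the check is one of set logic. Cross relatedness (to device, procedure or comparator) with seriousness and ask which kinds of event each definition admits.

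| Definition (SAP 7.10 a) | Unrelated, not serious | Unrelated, serious | Related, not serious | Related, serious |
|---|---|---|---|---|
| AE, first sentence | yes | yes | yes | yes |
| AE, second sentence | yes | no | no | no |
| SAE | no | yes | no | no |
| ADE | no | no | yes | no |
| SADE, by evident intent | no | no | no | yes, if anticipated |
| USADE | no | no | no | yes, if unanticipated |

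1. **AE.** The first sentence admits 4 of 4 kinds and the second admits 1 of 4, so both cannot hold. The rest of the section uses the broad sense. Assessing an adverse event for seriousness and device relationship would be pointless if it were non-serious and unrelated by definition, and the top grade of the relationship scale describes an adverse event shown to be device-related.

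2. **SAE.** It admits 1 of the 2 serious kinds. This holds whichever AE sentence governs, because the restriction is in the SAE definition itself. The number of serious events is SAE as defined + SADE + USADE, and no sentence in the SAP says that this sum will be reported.

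3. **SADE.** It is introduced as an adverse device effect, and an adverse device effect was defined one sentence earlier as not serious. The wording is inconsistent, although the intent (related, serious, anticipated) can be recovered from the end of the sentence.

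4. **Relatedness.** The classes need a yes-or-no answer, while the scale has six grades and none is tied to a class. A serious event graded Possible or Not assessable could therefore be an SAE or a SADE. In addition, every grade refers to the study device only, whereas ADE and SADE also cover procedure and comparator. The scale alone cannot identify an event related to scintigraphy.

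**The case against.** The strongest reply is that, apart from the first AE sentence, the definitions read as five mutually exclusive classes: AE (unrelated, not serious), SAE (unrelated, serious), ADE (related, not serious), SADE (related, serious, anticipated) and USADE (related, serious, unanticipated). All four kinds of event then have a class, all events are collected, and nothing disappears from the safety report if every class is tabulated. This part of the reply stands. A reader might infer that device-related events are lost, and the SAP does not support that.

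Two further inferences also go too far. One is that the AE incidence necessarily leaves out device-related events. That follows only if the second sentence governs, and much of the section uses the broad sense. The other is that the SADE count must be zero because an ADE cannot be serious. That reads a garbled sentence too literally, since the same sentence says that the event is serious.

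The reply does not remove the contradiction. The SAP never says that the classes are mutually exclusive, the first AE sentence says the opposite, and no ADE, SADE or USADE table is named. Nor is this detail left to the protocol, because the SAP states the definitions itself.

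**Conclusion.** The point holds in this form: the AE definitions conflict, so the planned AE incidence on the FAS may or may not include device-related and serious events. The SAE definition excludes every serious event related to the device, comparator or procedures, so an SAE count is not the count of all serious events. The SADE wording clashes with that of ADE.

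In kinds of event, the AE total spans 4 of 4 or 1 of 4 depending on the sentence used, and SAE spans 1 of 2. The SAP gives no event counts, so the effect on the reported numbers cannot be stated; it is nil if no related or serious event occurred. The agreement analyses, including the primary endpoint, are not affected. The conclusion rests on the SAP alone. The protocol's own definitions were not seen and may differ.

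**What to change.** 1. Delete the sentence stating that "AEs are non device related, non serious medical occurrences", so that AE means all untoward occurrences.
2. Either define SAE by seriousness alone, or keep the present restriction and state that the recorded classes are mutually exclusive.
3. Reword SADE as a related event that is serious and anticipated, so that it does not depend on ADE. Leave USADE as written; reducing it to unanticipated SADEs would narrow it.
4. Report three totals on the FAS, and state for each table which classes it counts:
   - all events;
   - all serious events = unrelated SAE + SADE + USADE;
   - all device-, procedure- or comparator-related events = non-serious ADE + SADE + USADE.

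   If SAE is defined by seriousness alone, the SAE row is already the serious total, and SADE and USADE must not be added to it again.
5. Before analysis, fix which relationship grades count as device-related. The SAP does not settle how to treat Not assessable, so the choice should be stated as a convention. Take procedure and comparator relatedness from the recorded class, because the scale covers the study device only.

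The cost is SAP wording and some summed rows. Enrolment was stopped at 167 subjects after the interim analysis (sections 7.8 and 7.12), so events may already carry a class; the totals above can be built from those classes without reclassifying events. The reported serious and related totals may look slightly less favourable.
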